8.0 SAFETY AND REPORTING

8.1 DEFINITIONS OF SERIOUS ADVERSE EVENTS AND ADVERSE EVENTS

8.1.1 ADVERSE EVENT

An Adverse Event (AE) is defined as any new untoward medical occurrence or worsening of a preexisting medical condition in a clinical investigation participant administered study drug and that does not necessarily have a causal relationship with this treatment. An AE can therefore be any unfavorable and unintended sign (such as an abnormal laboratory finding), symptom, or disease temporally associated with the use of investigational product, whether or not considered related to the investigational product.

The causal relationship to study drug is determined by a physician and should be used to assess all adverse events (AE). The causal relationship can be one of the following:

- Related: There is a reasonable causal relationship between study drug administration and the AE.
- Not related: There is not a reasonable causal relationship between study drug administration and the AE. The term "reasonable causal relationship" means there is evidence to suggest a causal relationship.

8.1.2 SERIOUS ADVERSE EVENTS

A **Serious Adverse Event (SAE)** is any untoward medical occurrence that at any dose:

- Results in death
- Is life-threatening (defined as an event in which the participant was at risk of death at the time of the event; it does not refer to an event which hypothetically might have caused death if it were more severe)
- Requires inpatient hospitalization or causes prolongation of existing hospitalization (see **NOTE** below)
- Results in persistent or significant disability/incapacity
- Is a congenital anomaly/birth defect
- Is an important medical event (defined as a medical event(s) that may not be immediately life-threatening or result in death or hospitalization but, based upon appropriate medical and scientific judgment, may jeopardize the subject or may require intervention [eg, medical, surgical] to prevent one of the other serious outcomes listed in the definition above.) Examples of such events include, but are not limited to, intensive treatment in an emergency room or at home for allergic bronchospasm; blood dyscrasias or convulsions that do not result in hospitalization.)
- Suspected transmission of an infectious agent (eg, pathogenic or nonpathogenic) via the study drug is an SAE

Although pregnancy and potential drug-induced liver injury (DILI), are not always serious by regulatory definition, however, these events must be reported within the SAEs timeline.

Any component of a study endpoint that is considered related to study therapy should be reported as an SAE (eg, death is an endpoint, if death occurred due to anaphylaxis, anaphylaxis must be reported).

NOTE: (PI determines if this information regarding hospitalizations are considered SAEs and should be included in the protocol. This is supplemental information that is included in BMS-sponsored trials)

8.1.3 NON-SERIOUS ADVERSE EVENT

A **non-serious adverse event** is an AE not classified as serious.

Non-serious Adverse Events are to be provided to BMS in aggregate via interim or final study reports as specified in the agreement or, if a regulatory requirement [e.g. IND US trial] as part of an annual reporting requirement.

8.1.4 NON-SERIOUS ADVERSE EVENT COLLECTION AND REPORTING

The collection of non-serious AE information should begin upon the signing of informed consent. All non-serious adverse events (not only those deemed to be treatment-related) should be collected continuously during the treatment period and for a minimum of 30 days following the last dose of study treatment.

Non-serious AEs should be followed to resolution or stabilization, or reported as SAEs if they become serious. Follow-up is also required for non-serious AEs that cause interruption or discontinuation of study drug and for those present at the end of study treatment as appropriate.

8.2 OVERDOSE

For purposes of this trial an overdose is defined as the accidental or intentional administration of any dose of a product that is considered both excessive and medically important. All occurrences of overdose must be reported as an SAE as well as a deviation from protocol.

All reports of overdose with and without an adverse event must be reported within 24 hours to the University of Cincinnati PI and to BMS Global Pharmacovigilance (Attn: [contact] [contact])

8.3 PREGNANCY AND LACTATION

If, following initiation of the investigational product, it is subsequently discovered that a study participant is pregnant or may have been pregnant at the time of investigational product exposure, including during at least 5 half-lives after product administration, the investigational product will be permanently discontinued in an appropriate manner (e.g., dose tapering if necessary for participant).

The investigator must immediately notify the University of Cincinnati PI and BMS at [contact] of this event via the Pregnancy Surveillance Form in accordance with SAE reporting procedures.

Protocol-required procedures for study discontinuation and follow-up must be performed on the participant.

Follow-up information regarding the course of the pregnancy, including perinatal and neonatal outcome and, where applicable, offspring information must be reported on the Pregnancy Surveillance Form [provided upon request from BMS].

Any pregnancy that occurs in a female partner of a male study participant should be reported to BMS and the University of Cincinnati PI. Information on this pregnancy will be collected on the Pregnancy Surveillance Form. In order to collect any pregnancy surveillance information from the female partner, the female partner must sign an informed consent form for disclosure of this information. Such events must be reported within 24 hours to the University of Cincinnati PI and within 24 hours to BMS Global Pharmacovigilance (Attn: [contact] [contact])

8.4 LAB ABNORMALITIES

All laboratory test results captured, as part of the study should be recorded following institutional procedures. Test results that constitute SAEs should be documented and reported as such.

The following laboratory abnormalities should be documented and reported appropriately:

- Any laboratory test result that is clinically significant or meets the definition of an SAE
- Any laboratory abnormality that required the participant to have study drug discontinued or interrupted
- Any laboratory abnormality that required the subject to receive specific corrective therapy.

It is expected that wherever possible, the clinical rather than laboratory term would be used by the reporting investigator (e.g., anemia versus low hemoglobin value).

8.5 POTENTIAL DRUG INDUCED LIVER INJURY (DILI)

Potential drug induced liver injury is defined as:

- 1) AT (ALT or AST) elevation > 3 times upper limit of normal (ULN)

AND

- 2) Total bilirubin > 2 times ULN, without initial findings of cholestasis (elevated serum alkaline phosphatase),

AND

- 3) No other immediately apparent possible causes of AT elevation and hyperbilirubinemia, including, but not limited to, viral hepatitis, pre-existing chronic or acute liver disease, or the administration of other drug(s) known to be hepatotoxic.

Wherever possible, timely confirmation of initial liver related- laboratory abnormalities should occur prior to the reporting of a potential DILI event. All occurrences of potential DILIs, meeting the defined criteria, must be reported as SAEs.

8.6 OTHER SAFETY CONSIDERATIONS

Any significant worsening noted during interim or final physical examinations, electrocardiograms, x-rays-, and any other potential safety assessments, whether or not these procedures are required by the protocol, should also be recorded as a non-serious or serious AE, as appropriate, and reported accordingly.

8.7 REPORTING ADVERSE EVENTS

All Serious Adverse Events (SAEs) that occur following the subject's written consent to participate in the study through 100 days of discontinuation of dosing must be reported to BMS Worldwide Safety. If applicable, SAEs must be collected that relate to any later protocol-specified procedure (e.g., a follow-up skin biopsy).

If the BMS safety address is not included in the protocol document (e.g., multicenter studies where events are reported centrally), the procedure for safety reporting must be reviewed/approved by the

BMS Protocol Manager. Procedures for such reporting must be reviewed and approved by BMS prior to study activation.

A MedWatch or CIOMS SAE form may be used to report SAEs. The BMS protocol ID number must be included on whatever form is submitted by the Sponsor/Investigator. The CIOMS form is available at: <http://www.cioms.ch/index.php/cioms-form-i>.

Following the subject's written consent to participate in the study, all SAEs, whether related or not related to study drug, are collected, including those thought to be associated with protocol-specified procedures. The investigator should report any SAE occurring after these time periods that is believed to be related to study drug or protocol-specified procedure. The duration of SAE collection should be extended to:

- 100 days for Nivolumab

For studies with long-term follow-up periods in which safety data are being reported, include the timing of SAE collection

The Sponsor will reconcile the clinical database SAE cases transmitted to BMS Global Pharmacovigilance ([contact]). Frequency of reconciliation should be every 3 months and prior to the database lock or final data summary. BMS GPV&E will email, upon request from the Investigator, the GPV&E reconciliation report. Requests for reconciliation should be sent to [contact]. The data elements listed on the GPV&E reconciliation report will be used for case identification purposes. If the Investigator determines a case was not transmitted to BMS GPV&E, the case should be sent immediately to BMS.

In accordance with local regulations, BMS will notify the study sponsor all reported SAEs that are suspected (related to the investigational product) and unexpected (i.e., not previously described in the IB). In the European Union (EU), an event meeting these criteria is termed a Suspected, Unexpected Serious Adverse Reaction (SUSAR). Investigator notification of these events will be in the form of an expedited safety report (ESR).

Other important findings which may be reported by BMS as an ESR include: increased frequency of a clinically significant expected SAE, an SAE considered associated with study procedures that could modify the conduct of the study, lack of efficacy that poses significant hazard to study subjects, clinically significant safety finding from a nonclinical (e.g., animal) study, important safety recommendations from a study data monitoring committee, or sponsor decision to end or temporarily halt a clinical study for safety reasons.

Upon receiving an ESR from BMS, the investigator must review and retain the ESR with the IB. Where required by local regulations or when there is a central IRB/IEC for the study, the sponsor will submit the ESR to the appropriate IRB/IEC. The investigator and IRB/IEC will determine if the informed consent requires revision. The investigator should also comply with the IRB/IEC procedures for reporting any other safety information.

In addition, suspected serious adverse reactions (whether expected or unexpected) shall be reported by BMS to the relevant competent health authorities in all concerned countries according to local regulations (either as expedited and/or in aggregate reports).

SAEs, whether related or not related to study drug, and pregnancies must be reported to BMS within 24 hours. SAEs must be recorded on BMS or an approved form; pregnancies must be reported on a Pregnancy Surveillance Form.

SAE Email Address: [contact]

SAE [contact]

If only limited information is initially available, follow-up reports are required. (Note: Follow-up SAE reports should include the same investigator term(s) initially reported.)

If an ongoing SAE changes in its intensity or relationship to study drug or if new information becomes available, a follow-up SAE report should be sent within 24 hours to BMS (or designee) using the same procedure used for transmitting the initial SAE report.

All SAEs should be followed to resolution or stabilization.

For studies conducted under an Investigator IND in the US, any event that is both serious and unexpected must be reported to the Food and Drug Administration (FDA) as soon as possible and no later than 7 days (for a death or life-threatening event) or 15 days (for all other SAEs) after the investigator's or institution's initial receipt of the information. BMS will be provided with a simultaneous copy of all adverse events filed with the FDA.

SAEs should be reported on MedWatch Form 3500A, which can be accessed at: <http://www.accessdata.fda.gov/scripts/medwatch/>.

MedWatch SAE forms should be sent to the FDA at:
MEDWATCH
[name]
[name]
Fax: [name] ([name])
<http://www.accessdata.fda.gov/scripts/medwatch/>

An SAE report should be completed for any event where doubt exists regarding its seriousness. For studies with long-term follow-up periods in which safety data are being reported, include the timing of SAE collection in the protocol.

If the investigator believes that an SAE is not related to study drug, but is potentially related to the conditions of the study (such as withdrawal of previous therapy or a complication of a study procedure), the relationship should be specified in the narrative section of the SAE Report Form.

If only limited information is initially available, follow-up reports are required. (Note: Followup SAE reports should include the same investigator term(s) initially reported.)

If an ongoing SAE changes in its intensity or relationship to study drug or if new information becomes available, a follow-up SAE report should be sent within 24 hours to BMS using the same procedure used for transmitting the initial SAE report. All SAEs should be followed to resolution or stabilization. All SAEs should be followed to resolution or stabilization.

8.8 EVALUATING ADVERSE EVENTS

An investigator who is a qualified physician will evaluate all adverse events according to the NCI Common Terminology for Adverse Events (CTCAE), version 5.0. Any adverse event which changes CTCAE grade over the course of a given episode will have each change of grade recorded on the adverse event case report forms/worksheets.

All adverse events regardless of CTCAE grade must also be evaluated for seriousness.

8.9 ADVERSE EVENT COLLECTION AND REPORTING

Non-serious AEs and SAEs whether or not related to the BMS product associated to this study, pregnancies, AEs associated with maternal exposure, and pregnancy outcomes ascertained in the study must be reported individually in the time frames noted below. All AEs collected will also be reported in aggregate in the final study report.

Any component of a study endpoint that is considered related to study therapy (e.g., death is an endpoint, if death occurred due to anaphylaxis, anaphylaxis must be reported) should be reported as an SAE.

8.9.1 SERIOUS ADVERSE EVENT COLLECTION AND REPORTING

Following the subject's written consent to participate in the study, all SAEs, whether or not related to the BMS product associated with this study, must be collected, including those thought to be associated with protocol-specified procedures. SAEs must be recorded on the Solicited and Non-interventional Research AE/SAE Form and reported to BMS (or designee) within 24 hours/1 business day to comply with regulatory requirements. A form should be completed for any event where doubt exists regarding its status of seriousness. Although overdose and cancer are not always serious by regulatory definition, these events should be recorded on a form and reported to BMS within 24 hours/1 business day.

Investigators should report to the responsible regulatory authority as appropriate.

All SAEs must be reported by confirmed facsimile (fax) transmission or reported via electronic mail to Medwatch and BMS. Information for contacting BMS is as follows:

SAE Email Address: [contact]

SAE [contact]

If only limited information is initially available, follow-up reports may be required.

For studies capturing SAEs through electronic data capture (EDC), electronic submission is the required method for reporting. The paper forms should be used and submitted immediately, only in the event the electronic system is unavailable for transmission. When paper forms are used, the original paper forms are to remain on site.

If it is discovered a patient is pregnant or may have been pregnant at the time of exposure to the BMS product associated with this study, the pregnancy, AEs associated with maternal exposure and pregnancy outcomes must be recorded on a Pregnancy Surveillance Form and reported to BMS (or designee) within 24 hours/1 business day by confirmed fax or reported via electronic mail to [contact]. If only limited information is initially available, follow-up reports may be required. The original BMS forms are to remain on site. Follow-up information should be obtained on pregnancy outcomes for one year following the birth of the offspring.

Any pregnancy that occurs in a female partner of a male study participant should be reported to BMS. Information on this pregnancy will be collected on the Pregnancy Surveillance Form.

9.0 STATISTICAL ANALYSIS PLAN

9.1 EFFICACY ANALYSIS

All patients who received ≥ 1 dose of Nivolumab will be assessed of efficacy and the primary and secondary endpoints of efficacy will be disease-free survival (DFS) at 2- and 1-year, respectively. DFS is defined as the duration from the time of treatment allocation to the time of discovery of the first evidence after treatment of any tumor (local, regional, metastatic, or second primary) or death from any cause. The distribution of DFS will be summarized by Kaplan-Meier curve, and the median DFS and its associated 95% confidence interval (CI) will be calculated. The DFS at 1- and 2-years will be also summarized with its associated 95% CIs. In addition, patients will be censored at the end of the study, and both disease free survival (or DFS defined as no recurrence by the time of censoring) and overall survival (OS, defined as being alive by the time of censoring) will be assessed using Kaplan-Meier curves.

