All patients who received ≥ 1 dose of Nivolumab will be assessed for efficacy and the primary and secondary endpoints for efficacy will be disease-free survival (DFS) at 2- and 1-year, respectively. DFS is defined as the duration from the time of treatment allocation to the time of discovery of the first evidence after initiation of investigational treatment of any tumor (local, regional, metastatic, or second primary) or death from any cause. The distribution of DFS will be summarized by Kaplan-Meier curve, and the median DFS and its associated 95% confidence interval (CI) will be calculated. The DFS at 1- and 2-years will also be summarized with its associated 95% CIs. In addition, patients will be censored at the end of the study (end of two years of follow-up of last patient enrolled), and both disease free survival (or DFS defined as no recurrence by the time of censoring) and overall survival (OS, defined as being alive by the time of censoring) will be assessed using Kaplan-Meier curves.

Safety Analyses:

The All-Patients-as-Treated (APaT) population will be employed for safety analyses. The secondary safety endpoints are the Grade 3 and 4 adverse events and the all adverse event graded from 1 to 5. Both safety secondary endpoints are dichotomous and will be summarized using frequency (in %). In addition, the 95% CI's will be calculated using the exact method, i.e. the binomial distribution method. We expect to reach 13% of Grade 3 and 4 adverse events and 58.9% of all Graded Adverse events, similar to those reported in the Checkmate 141 study.

Biomarker Assessments:

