9.5 STATISTICAL ANALYSIS PLAN FOR ENDPOINTS

9.5.1 EFFICACY ENDPOINTS

Primary and secondary endpoints of efficacy are 2-year and 1-year DFS, respectively. DFS will be defined as the duration from the time of treatment allocation to the time of discovery of the first evidence after treatment of any tumor (local, regional, metastatic, or second primary) or death from any cause.

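### The additional end-of-study Kaplan-Meier curve is labelled DFS but defined by recurrence alone, which conflicts with the composite DFS definition in the same paragraph

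*Combined protocol and SAP*

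**What the plan says.** Section 9.1 first gives DFS as a composite, running from treatment allocation to first evidence of "any tumor (local, regional, metastatic, or second primary) or death from any cause". That definition governs the Kaplan-Meier summary, the median and the 1- and 2-year estimates described next. Sections 2.2 and 9.5.1 and the endpoint list in the synopsis use the same composite.

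The last sentence of the 9.1 paragraph adds another analysis. It opens "In addition, patients will be censored at the end of the study" and names two quantities for Kaplan-Meier curves. The first is disease-free survival, which a parenthesis glosses as "DFS defined as no recurrence by the time of censoring". The second is OS, which its own parenthesis ties to the patient still living at that point. The Efficacy Analyses paragraph of the synopsis has the same sentence, and explains that the end of the study is two years after the last enrolment.

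Section 9.6.1 says that Kaplan-Meier curves will assess DFS and OS, without saying which DFS is meant.

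**The concern.** One paragraph attaches two event sets to one name. The second leaves out death and does not clearly include second primaries. OS stands beside it defined by being alive, so a plain reading assigns deaths to OS and recurrences to DFS. The plan does not say whether, in this added analysis, a death without recurrence is an event, a censoring or a competing risk. Two analysts could follow 9.1 and produce different curves, both labelled DFS.

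The error can run only one way, because removing deaths from the event set raises the curve. What results is a time-to-recurrence quantity. For that, a Kaplan-Meier curve that censors deaths does not estimate the proportion free of recurrence in the presence of death, nor the proportion alive and disease-free.

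Deaths without a recorded recurrence are plausible in this trial. Follow-up imaging is required only on suspicion of relapse (7.5.7), follow-up may be by phone (7.7.4), and disease-status follow-up ends when non-study cancer treatment starts (4.5).

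**Working it through.** **1. The plan's own figures.** With exponential DFS, hazard = -ln(S)/2 per year.
- Null, S = 0.33: 0.5543. Alternative, S = 0.53: 0.3174. Hazard ratio 0.573.
- One-sample log-rank test, one-sided 5%, 80% power, 2 years of follow-up after accrual: a single-stage calculation gives n = 35 at 3 patients per month (power 80.4%) and 36 at 3.5-4 per month.
- Dropout: 35/0.9 = 38.9, so 39.

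The synopsis figures of 35 and 39 therefore reproduce from the stated 33% and 53%. Those are rates of DFS, which the plan formally defines as the composite. Settling the end-of-study wording changes none of them.

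**2. Size of the overstatement.** Let S be the true composite 2-year DFS and f the share of first events that are deaths without recurrence. The documents do not give f, so it is an assumption. With constant hazards and such deaths censored, the recurrence-only Kaplan-Meier value at 2 years is S^(1-f). For example, 0.53^0.80 = 0.602 and 0.33^0.80 = 0.412.

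| f | True 53% becomes | Excess (points) | True 33% becomes | Excess (points) |
|---|---|---|---|---|
| 5% | 54.7% | 1.7 | 34.9% | 1.9 |
| 10% | 56.5% | 3.5 | 36.9% | 3.9 |
| 20% | 60.2% | 7.2 | 41.2% | 8.2 |
| 30% | 64.1% | 11.1 | 46.0% | 13.0 |
| 50% | 72.8% | 19.8 | 57.4% | 24.4 |

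Over f = 5-20% the excess is about 2 to 8 points. Counting the deceased as recurrence-free to 2 years, instead of censoring them, would give more: 62.4% rather than 60.2% at f = 20% and a true 53%.

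**3. When the curve would pass overall survival.** Let L = -ln(S)/2 be the composite hazard and M = ln(2)/m the hazard of death after recurrence, where m is the median survival after recurrence in years (assumed; not in the documents). Then

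OS(2) = S + (1-f) × L × [exp(-2L) - exp(-2M)] / (M - L).

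Example: S = 0.53, f = 30%, m = 0.5. L = 0.3174 and M = 1.3863, so OS(2) = 0.53 + 0.70 × 0.3174 × (0.53 - 0.0625)/1.0689 = 0.627. The recurrence-only value is 0.641, just above it.

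Setting S^(1-f) equal to OS(2) gives the share above which the curve exceeds OS:

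| Median survival after recurrence | True DFS 53% | True DFS 33% |
|---|---|---|
| 6 months | 27% | 29% |
| 9 months | 34% | 36% |
| 12 months | 38% | 41% |

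At f of 20% or less the curve stayed below OS in every scenario run. Composite DFS can never exceed OS.

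**The case against.** The strongest reply is that the sentence is about administrative censoring and defines no endpoint. Its two parentheses are parallel: alive at the cut-off for OS, no recurrence at the cut-off for DFS. Both can be read as the status of a patient who reaches the end of the study event-free, and a patient who died earlier is not in that position. Read with the definition a few sentences before, the parenthesis may be loose shorthand. This reading is possible, but the text does not establish it, and 9.6.1 does not help. It is a reason to clear up the wording, not to leave it.

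A second reply stands in full: the composite governs the primary and secondary DFS estimates, and the parenthesis belongs only to an added analysis. A reader might infer that the one-sample log-rank test in 9.3 would also leave out deaths, or that the recurrence-only curve is meant to be set against the 33% null. Nothing in the documents connects them.

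A reader might also try to size the effect from the 28-patient series in section 2.1. Seven patients recurred within 12 months, so 21/28 = 75% had not. Twelve died over 2 years, so 16/28 = 57% survived. If no one relapsed after month 12, 2-year DFS lies between 9/28 = 32% and 57%, which suggests a gap of 18 to 43 points. The documents do not support that range:
- It sets a 12-month share against 2-year outcomes, and relapses after month 12 are not reported. With 12 or more relapses by 2 years, the crude no-recurrence share would be at most 16/28 and would not exceed OS.
- The upper end needs none of the seven who relapsed to have died, although section 2.2 calls relapse the most common cause of death.
- The lower end is not a floor. If every death followed a relapse, the gap would be zero.

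**Conclusion.** The concern holds in limited form. Section 9.1 and the synopsis contain two incompatible descriptions of DFS, and the one attached to the additional end-of-study curve, taken literally, omits deaths without recurrence. The 2-year overstatement would be about 2 to 8 percentage points if 5-20% of first events are such deaths, under constant hazards with those deaths censored. That share is assumed, and the figures do not cover second primaries.

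A curve labelled DFS lying above OS is possible but not the expected result. It needs roughly 27-41% or more of first events to be deaths without recurrence, with 6-12 months' median survival after recurrence also assumed.

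This is an inconsistency in a supplementary analysis. It should be corrected before the data are analysed, but it is not a fault in the primary endpoint, the hypothesis test or the sample size.

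**What to change.** In section 9.1 and in the Efficacy Analyses paragraph of the synopsis, delete the parenthesis that begins with the word or and continues "DFS defined as no recurrence by the time of censoring". State that every DFS curve, including the end-of-study one and those in 9.6.1, uses the composite of any tumor (including second primary) or death from any cause.

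If recurrence alone is of interest, add it under its own name, cumulative incidence of recurrence, and estimate it with death without recurrence as a competing risk.

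The cost is a wording change in two places and one clarifying sentence. The design stays at 35 evaluable and 39 enrolled, and no new data are needed.
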